Research Summary

Version Date: 06Jun2024

Protocol Title: Reducing Disparities in Medication Adherence of Patients with Systemic Lupus Erythematosus (SLE)

Department/Division/Clinical Setting: Division of Rheumatology & Immunology, Duke University Medical Center.

Key Personnel: PI: [name], MS. Instructor, Division of Rheumatology & Immunology, Duke University Medical Center.

CRC: [name]

Consultant: [name]

NCT ID: NCT06018350

Purpose of the Study:

The aims of this study are to:

- 1) Identify key contributors to medication nonadherence among minority SLE patients using mixed methods, including patient self-efficacy, patient-provider communication and racial discordance;
- 2) Develop a multi-level intervention directed towards providers, clinic staff, and patients based on concepts of self-affirmation and positive affect to increase medication adherence among minority SLE patients by addressing specific findings from Aim 1; and
- 3) Pilot test the intervention designed in Aim 2 to address barriers that originate in the clinical interaction in the Duke Lupus Clinics.

Background & Significance:

Systemic lupus erythematosus (SLE) is more common, severe, and deadly in Hispanics, Asians, and African Americans than in Caucasians. Medication non-adherence is more prevalent in ethnic minorities and may be a significant contributor to known outcome disparities. A range of barriers to adherence have been identified including factors both extrinsic (such as cost, insurance, medication complexity, side effects) and intrinsic (patient level factors, patient-provider relationship) to the patient encounter. This study will focus on two modifiable risk factors intrinsic to the clinical encounter that are especially relevant in the care of minority lupus patients: 1. *self-efficacy*, or confidence in one's own ability to take action to overcome barriers with regards to a specific behavior; and 2. effective *patient-provider communication*. Data suggest that both of these factors are diminished among minority populations, particularly when the patient and provider come from different cultural backgrounds.

Treating lupus, an incurable multisystem autoimmune disease, often requires long term use of immunosuppressive and immunomodulatory medications to prevent disease progression and damage. Barriers to adherence include both unpleasant medication side effects and incomplete efficacy, leading to frequent medication changes. Paradoxically, while troublesome symptoms like fatigue have no effective treatments, severe organ manifestations such as nephritis may be completely asymptomatic, leading patients to question the necessity of treatment escalation.

Additional patient-specific challenges such as self-management of physical activity, nutrition, medications, financial complications from medical care and disability, and stress reduction, make patient self-efficacy a critical management challenge. As a result of these many challenges, medication non-adherence is as high as 75% among patients with SLE. Such complexities make patient-centered lupus care and effective patient-provider communication crucial.

Further complicating medication adherence, the high rate of racial discordance between lupus patients and providers may pose barriers; while African-Americans comprise nearly 40% of SLE patients, they represent only 0.8% of US adult rheumatologists. Racial discordance is associated with stereotypical threat, or apprehension about being negatively stereotyped. This threat impairs patient-provider communication and decreases patient self-efficacy. Also, racial discordance has been linked to implicit bias in providers – unconscious attitudes or stereotypes that affect one's understanding, actions, and decisions, which can further impair communication.

All these factors are important because poor communication and low patient-self efficacy can both undermine patient-centered care, medication adherence and clinical outcomes. Lupus providers also experience stress as a result of patient non-adherence, which creates feelings of powerlessness, helplessness, and frustration that stem from a sense of lack of control. Poor patient outcomes that result from non-adherence may cause providers to question their self-image as a competent health care professional, making them more vulnerable to burnout. Such provider challenges can in turn negatively impact patient adherence. Psychological interventions aimed at *self-affirmation* (the act of affirming one's core values and sources of personal pride) and *positive affect* (feelings that reflect pleasurable engagement with the environment) enhance both patient-physician communication and patient self-efficacy by defusing stereotypical threat, buffering against stress, and reducing defensive rejection of information. Directing psychological interventions towards both lupus providers and patients is a promising strategy to improve adherence and reduce outcome disparities; randomized controlled trials demonstrate that promoting self-affirmation and positive affect improves medication adherence and health behaviors among patients and improves performance among students and professionals.

Despite the clear morbidity that stems from medication non-adherence, few studies have investigated determinants of non-adherence in SLE. This knowledge gap is even wider for minority populations. Our proposal will begin to fill this gap by studying the relationship between race, patient-provider communication, patient self-efficacy in taking lupus medicines, and medication adherence in SLE patients.

Methods:

Aim 1: Mixed Methods Approach to Identify Key Barriers of Medication Adherence

a. Quantitative study: We will analyze data already collected through the Duke Lupus Registry (DLR) (Pro00008875) and Sub-studies of the DLR (Pro00094645). The following table shows cross-sectional data that are collected by self-report. We anticipate analyzing data from 124 consecutively enrolled participants. In addition, the DLR has also collected information from medical records including: insurance, medication details, disease duration, missed visits, hospitalizations/emergency room visits in the past 12 months, comorbidities, medication refill data and drug levels of hydroxychloroquine, azathioprine, and mycophenolate mofetil when available. The Systemic Lupus Activity Questionnaire (SLAQ), a patient reported disease activity

measure, and Systemic Lupus Erythematosus Disease Activity Index (SLEDAI), a provider derived lupus disease activity measure, both routinely collected at each visit in Duke Lupus Clinic, will also be included.

Self-report data:

Demographics	Age, Gender, race/ethnicity, employment status, marital status, living arrangement will be ascertained by self-report
Medication Adherence Self-Report Inventory (MASRI) Part A	A 6-item questionnaire about the amount of medication taken. Provides a numerical estimate of adherence from 0-100%. Validated in lupus.
Patient-Reported Outcomes Measurement Information System (PROMIS) Self-Efficacy for Managing Medications and Treatments – Short Form 8a	An 8-item on a 5-point Likert scale measuring patient confidence in taking medications in a variety of situations.
PROMIS General Self-Efficacy – Short Form 4a	A 4-item on a 5-point Likert scale measuring general level of confidence in managing various situations, problems, and events.
Interpersonal Process of Care Survey (IPC)	A multidimensional instrument measuring communication, patient-centered decision making, and interpersonal style using 29 items on a 5-point Likert scale.
Positive and Negative Affect Schedule (PANAS)	Two 10-item mood scales measuring positive and negative affect on a 5-point scale.
PROMIS-29	Measures 7 domains with 29 items: physical function, anxiety, depression, fatigue, sleep disturbance, social function, and pain. Validated in SLE.

Statistical Analysis: Adherence based on self-report will be analyzed as a continuous variable from 0-100%. Adherence as a binary variable based on a cutoff of $\geq 80\%$ will also be explored. Patient self-efficacy and patient-physician communication will be analyzed as continuous variables. We will also explore analyzing them as binary variables dichotomized at the median to high vs. low. Disease activity will be categorized as remission, low, medium, and high. The association between medication adherence as a continuous variable and 1) patient self-efficacy and 2) patient-provider communication will be assessed using linear regression models.

b. Qualitative study: We will conduct individual interviews with minority lupus clinic patients, clinical staff and providers to better understand facilitating factors and barriers to adherence with a focus on patient-physician communication and patient self-efficacy. We will also measure provider stress and implicit bias using the implicit association test

(<https://implicit.harvard.edu/implicit/>). Prior to start of interviews, each participant will complete a brief questionnaire that include basic demographic information from the participants including age, gender, race/ethnicity, education, years since disease diagnosis for patients, years of being a rheumatologist for providers.

Inclusion: Patients are eligible if they are non-Caucasian, have an established diagnosis of SLE, actively followed in the Duke Lupus Clinic for at least 6 months, and are prescribed at least 1 scheduled oral or injectable disease modifying medication for lupus. All clinic staff and providers are eligible.

Exclusion: we will exclude patients who are pregnant or nursing, seen for the first time in Duke Lupus Clinic, and those with significant cognitive impairment as determined by treating rheumatologist.

Sampling Strategy and recruitment: Two purposeful samples of 1) lupus clinical staff and providers, and 2) patients with SLE will be studied. Recruitment will continue until idea

saturation, typically by 12 subjects in a group. We will review patients' records to identify potential participants to invite them for the interview based on demographics and adherence data (obtained from their pharmacy). A recruitment phone script will be used, and potential participants will be contacted prior to their visit to lupus clinic.

Research Design and Subject Compensation: Semi-structured interviews will be conducted using an IRB approved interview guide.

In-person Consent: Consenting patients will complete the interview, before, on or after the day of the lupus clinic visit, in person or either over the phone. If the patient interview is conducted over the phone, consent will take place at the time of the lupus clinic appointment and the interview will be scheduled as a phone call using the IRB approved interview document. Regardless of when the interview takes place, the consent will occur in person prior to the interview.

Email consent: In order to facilitate recruitment in a timely manner, the consent and the IRB disclosure form may be emailed to the participant. If the participant elects to complete the in-person interview, the consent and IRB disclosure form will be returned to the study staff on the day of the interview. A member of the study team will sign the consent and provide the participant with their signed and dated copy prior to the interview. If the participant elects to complete a phone interview, the interview will not be scheduled until the consent and IRB disclosure form have been emailed to the study PI. The study PI will sign the consent and send a signed and dated copy back to the participant. Once the consent and IRB disclosure form are printed, the PI will delete the email. Clinic staff and providers will complete their interviews either in-person or over the phone. Each interview will take 30-60 minutes.

Compensation: A \$25 stipend will be offered to each patient as an appreciation of his/her time. Clinic staff and providers will not be compensated.

Data Analysis & Statistical Considerations: We will use qualitative, thematic analysis. Interviews will be audio-recorded and transcribed verbatim. The recordings will be transcribed by GMR Transcription. Nvivo, a qualitative research software, will be used to facilitate analysis. Two analysts from Duke QualCore will apply deductive, structural codes, followed by inductive, thematic codes to the data. We will then identify the most salient themes, further explore the nuances of each theme and how they relate to each other as well as identify sub-themes, primarily based on salience.

Aim 2: Intervention Development

Based on findings from the first aim of the study, a multi-disciplinary team will develop a multi-level intervention. We will invite some clinic patients to be part of the advisory group that will develop the intervention. The patients will be collaborators as opposed to research subjects. The PI will present the data learned from Aim 1 and get their input on the intervention that will be developed. Since the patients are the true stakeholders, their input is extremely valuable on what would work/not work. We will seek to identify new approaches physicians can use to communicate with minority patients more effectively. Any component of the intervention directed at the patient will be delivered at the beginning of the clinical encounter after obtaining informed consent. The intervention will most likely focus on provider-patient communication and self-efficacy, but will be driven by data from Aim 1. The target population will also be determined based on Aim 1 data.

Study Team: The intervention will be developed in collaboration with lupus clinic providers, staff, and patients. We will convene 3-6 monthly meetings to review results from Aim 1, identify targets for intervention, and develop feasible and acceptable interventions.

Intervention Targets: We hypothesize that an intervention that involves self-affirmations and positive affect for physicians, staff, and patients will improve provider-patient communication and enhance patient self-efficacy. It is possible, however, that Aim 1 will not demonstrate these factors as important in the racial disparities in medication adherence. If this were to happen, we would work with the multi-disciplinary team to identify different targets and interventions that would be more effective, based on the results of Aim 1.

Aim 3: Pilot Testing of Intervention

The intervention developed from Aim 2 of the study will be implemented in clinic, focusing on a small cohort of providers, clinic staff, and African American SLE patients. The baseline measures collected in the Aim 1 surveys will be collected at the time of the intervention and again 3 months later. Feasibility and acceptability of the intervention will be assessed. At the completion of this pilot, we will have feasibility and outcomes measures to adjust or expand the intervention project.

IRB amendment 15Jan2020

Based on our findings from Aim 1, our intervention will involve all providers in the Duke Lupus Clinic and will not need informed consent. When the protocol was first written we thought the intervention would enroll patients, but instead we have decided to apply our intervention through the Duke Lupus Clinic.

INTERVENTION:

During a routine standard of care clinic visit, the provider is prompted by a smartphrase in Epic EMR to share the screen with their patient and review their lupus medication refill information available through connection with Surescript. Positive feedback is provided to patients with proportion of days covered in the goal range of 80-100%. For those with proportion of days covered <80%, barriers are explored with open-ended questions. Adherence barriers elicited during this conversation are then addressed and documented in Epic. Acceptability is assessed using anonymous provider surveys, and feasibility is measured by percentage of visits with adherence documentation in Epic EMR. We will also explore effect on patient-reported adherence and pharmacy refill rates 3 months after the intervention. The intervention will be conducted from October 1, 2019 to January 31, 2020. Chart review of patients enrolled in the Duke Lupus Registry from this period and 3 months after will be performed to assess the intervention.

Consent Process

Quantitative data analysis: The consent form for the DLR includes use of medical information.

Qualitative study: Participants will provide signed informed consent prior to participation in individual interviews. The consent process will include an explanation of the project design and intent, an assurance of confidentiality and data security, and a reminder that participation is voluntary. When each participant is invited, it will be clear that this is a research study and their responses will be used for research. Consent will be conducted by Study PI, study interviewer and/or CRC's.

Pilot intervention: Details of the intervention will be dependent on our findings from Aim 1. An addendum to the IRB with details of the intervention will be submitted prior to start of this phase of the study. If consent is applicable, it will also be submitted through process of an amendment.

Subject's Capacity to Give Legally Effective Consent: Patients who are not competent to provide informed consent in English will not be included.

Study Interventions: To be determined based on findings from Aim 1. Updated 15Jan2020 as above.

Risk/Benefit Assessment: Being included in this study does not pose any increased risk to participants involved. There is minimal potential risk for loss of confidentiality. Patients who participate in the intervention may experience improved patient-physician communication, self-efficacy, and/or medication adherence. The data obtained, may improve the care for patients with SLE in the future. The risk to each participant in this study is no greater than minimal, making it reasonable given the potential benefit to future patients.

Costs to the Subject: None

Data & Safety Monitoring: A data monitoring committee will not be used.

Privacy, Data Storage & Confidentiality: All data including the audiotapes and transcriptions will be maintained on a secure server. Participants will be assigned a unique identification number that will not be related to their name, date of birth, social security number, or medical record number. For data analysis, the unique ID number will be the only patient identifier used.

IRB Amendment 06Jun2024

We will assess change in medication adherence by comparing Medication Possession Ratio (MPR) of patients seen during the intervention period by participating providers. To do this, we will obtain medication fill data using chart review and by pulling data directly from the EMR. We will use the Analytics Center of Excellence (ACE) to pull data from the EMR to include encounter date, patient demographics, medications, and Surescripts refill data.

Data will include return patients seen by the following participating providers on the dates specified:

[name]: 2/16, 2/23, 3/1, 3/8

[name]: 2/26, 2/28, 3/4, 3/11, 3/13, 3/18, 3/20

[name]: 2/13, 2/15, 2/20, 2/22, 2/27, 2/29, 3/5, 3/7

[name]: 2/15, 2/22, 2/29, 3/7

[name]: 2/23, 3/8, 3/22

[name]: 2/15, 2/29, 3/14, 3/21

Data will be delivered securely via Box.

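### Aim 1a fits a 0-100% adherence score by linear regression with no robust variance, so the slope's interval could be too narrow or too wide if scores bunch near 100%

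*Combined protocol and SAP*

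**What the plan says.** All of this is in the Aim 1 quantitative study (part a) of the combined protocol and SAP.

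- **Outcome.** The self-report data table lists MASRI Part A, six items: "Provides a numerical estimate of adherence from 0-100" per cent. The Statistical Analysis paragraph keeps that scale: "Adherence based on self-report will be analyzed as a continuous variable from 0-100" per cent.
- **Predictors.** "Patient self-efficacy and patient-physician communication will be analyzed as continuous variables". In the table these come from Likert instruments with five response points.
- **Model.** The associations "will be assessed using linear regression models". The plan names no variance estimator, transformation, bounded-outcome model or residual check.
- **Secondary looks.** "Adherence as a binary variable based on a cutoff of" 80% or more is to be explored, as are the predictors split at their medians.
- **Size.** "We anticipate analyzing data from 124 consecutively enrolled participants". No alpha, power, effect size or standard deviation goes with this number.
- **Level of adherence.** The only background figure is that "medication non-adherence is as high as 75% among patients with SLE". No mean, SD or share of patients at 100% is given.

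**The concern.** A score that cannot exceed 100 must lose spread as its mean approaches 100. If self-efficacy or communication moves the mean, patients at one end of the predictor vary much less than those at the other. The standard error that software reports by default for a linear regression assumes equal spread. How far it errs, and in which direction, depends on which patients carry the leverage.

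At stake is how precisely the two Aim 1a slopes are reported. Self-efficacy and communication are the two factors the study is built around, and Aim 2 says the choice of intervention is to follow the Aim 1 data. An interval of the wrong width misstates how well those associations are known.

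**Working it through.** The plan has no power or precision figure to reproduce. The check is whether the default interval is reliable at n = 124.

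**Inputs from the documents:** bounded 0-100% outcome, continuous predictors, linear regression, n = 124. **Assumed, because the documents are silent:** every distribution below.

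**1. Why the direction can vary.** For one predictor, the usual variance of the slope is s² / Σ(xᵢ − x̄)². The actual variance is Σ(xᵢ − x̄)²σᵢ² / [Σ(xᵢ − x̄)²]². The usual one is too small when σᵢ² is large where (xᵢ − x̄)² is large, and too big in the opposite case. If adherence is unrelated to x, σᵢ² does not vary with x and the two agree. HC3 replaces σᵢ² by eᵢ²/(1 − hᵢ)², where hᵢ is the leverage, and so follows the actual variance in both cases.

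**2. How unequal the spread can be.** Take a beta-distributed outcome with mean m = 1/(1 + exp(−(a + bx))) and variance m(1 − m)/(1 + φ), with a = 1.7, b = 0.6, φ = 3.

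- At x = −2 SD: m = 1/(1 + e^−0.5) = 0.622; SD = √(0.622 × 0.378 / 4) = 0.242, or 24 points.
- At x = +1 SD: m = 1/(1 + e^−2.3) = 0.909; SD = √(0.909 × 0.091 / 4) = 0.144, or 14 points.

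The variance ratio is (0.242/0.144)² ≈ 2.8. If the predictor bunches at its upper end, the few low scorers have both the leverage and the large variance, so the default SE is too small. If it bunches at its lower end, the leverage sits with the low-variance patients, so the default SE is too large.

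**3. Coverage at n = 124.** The outcome is as in step 2, rounded to 5%, with (a, b, φ) = (1.7, 0.6, 3), (1.7, 0.9, 3), (2.0, 0.6, 2) and (1.4, 0.5, 3). Mean adherence is then 79-87%, with 22-49% of patients at 100%. There were 4,000 trials per setting, and coverage is for the population least-squares slope. The upper-bunched predictor is Beta(5, 1.2).

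| Predictor | Usual 95% interval | HC3 interval |
|---|---|---|
| Bunched at upper end | 89-92% | about 94% |
| Symmetric (normal) | 93-95% | about 94-95% |
| Right-skewed | about 97% | about 95-96% |
| Any shape, no association | about 95% | about 95% |

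Monte Carlo error is about ±1 point (at 90%: 1.96 × √(0.9 × 0.1/4000) = 0.9 points). HC3 was lowest, at about 93%, in the upper-bunched setting with nearly half of patients at 100%.

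In the upper-bunched case the usual SE was 0.82-0.89 of the true SD of the slope. A correct interval would be 1/0.89 = 1.12 to 1/0.82 = 1.22 times as wide.

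**4. A different generator.** Here the outcome was normal with SD 20, clipped to 0-100, with about 7-60% of patients at 100%, slopes of 0, 5 or 10 points per SD, and 8,000 trials per setting. Usual coverage was 83.0-94.6% with a left-skewed or ceilinged predictor, 92.0-96.0% with a normal one and 96.0-97.9% with a right-skewed one. With zero slope the type I error was 4.7-5.4%. HC3 covered 92.5-95.9% throughout. The pattern is the same.

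**5. Without the ceiling.** With the beta generator, b = 0.6, φ = 3 and mean adherence of only 50-62%, the usual interval covered 95-97% for every predictor shape. The shortfall needs a ceiling, a true slope and, for the most part, an upper-bunched predictor together.

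**The case against.** The strongest reply is that nothing in the documents shows a ceiling or a skewed predictor; the quoted non-adherence figure, if anything, points away from a ceiling. The plan is also silent on the variance estimator, so it does not commit to the default one. Both points stand: this is an unspecified detail with a conditional consequence, not a demonstrated error. The exploratory analysis at 80% and the median splits are a partial offset, since neither relies on a straight line over the whole scale. They discard information, however, and do not correct the continuous analysis.

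Four stronger readings are tempting, and the documents do not support them.

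- **That a ceiling by itself makes the interval too narrow.** Coverage is nominal with no association, close to nominal with a symmetric predictor in most settings, and too high with a right-skewed one.
- **That these slopes decide the intervention targets.** Aim 1 is mixed-methods, Aim 2 has a multidisciplinary team with patient advisers review its results, and no alpha or decision threshold is set. The 15Jan2020 amendment shows that the intervention has already been chosen.
- **That fitted values above 100% are a material defect.** Up to 6.5% of them exceeded 100% with a normal predictor, but the aim is association and nothing is predicted.
- **That the slope is biased.** A ceiling flattens it relative to an uncapped latent scale: in one clipped-normal setting with about 40% at 100%, a latent slope of 10 was estimated as 5.9. The plan's outcome is the reported percentage, and it defines no latent scale, so this is not an error in what it sets out to estimate. Robust intervals would not change it.

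**Conclusion.** The point holds as a minor one. The plan regresses a bounded score linearly and does not say how the variance will be estimated. If scores bunch near 100% and are truly associated with the predictor, the default interval may cover about 89-92% (predictor bunched at its upper end), 93-95% (symmetric) or about 97% (right-skewed) instead of 95%. Harsher assumptions, with about 60% of patients at 100%, took it as low as 83%. Bunching at the upper end is plausible for confidence and communication ratings, but it is not documented.

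The consequence is misstated precision, not spurious findings. In the four upper-bunched settings of the beta simulation, a zero slope was rejected in 98-100% of trials with the usual SE and 96-100% with HC3, and those associations were real. Because Aim 1a is cross-sectional and exploratory, has no stated power, and is one input among several, the point does not threaten the study's conclusions.

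**What to change.** Keep the linear regression and its slope in percentage points, and add to the Statistical Analysis paragraph that confidence intervals will use HC3 standard errors (or a bootstrap). This does not require knowing in advance which way the default would err. Report the mean, the SD and the share of patients at 100% for adherence, and the distributions of the two predictors, so that a reader can see whether the issue arises.

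Optionally, add a fractional-logit model of adherence/100 with robust standard errors as a sensitivity analysis, reported as average marginal effects in percentage points per SD. Replacing the linear model outright would be a matter of preference.

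The cost is one sentence and one software option, on data the registry already holds. Intervals may become somewhat wider. As the intervention has already been chosen, the benefit is to the reporting or re-analysis of the Aim 1a slopes.
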